2. LIST OF ABBREVIATIONS

See Medicine Glossary:

<http://glossary>

| Term | Definition / description |
|-------|---|
| ALT | Alanine Aminotransferase |
| AST | Aspartate Aminotransferase |
| BMI | Body mass index |
| CSFT | Central Subfield Thickness |
| CV | Arithmetic Coefficient of Variation |
| DBLM | Database Lock Meeting |
| DLE | Dose Limiting Event |
| ES | Enrolled Set |
| EOT | End of Trial |
| FAS | Full Analysis Set |
| gCV | Geometric Coefficient of Variation |
| gMean | Geometric Mean |
| IOP | Intraocular Pressure |
| iPD | Important Protocol Deviation |
| IQRMP | Integrated Quality and Risk Management Plan |
| IRF | Intra-retinal Fluid |
| IVT | Intravitreal |
| LLT | Lower Level Term |
| Max | Maximum |
| Min | Minimum |
| MRD | Multiple Rising Dose |
| N | Number of non-missing observations |
| OCT | Optical Coherence Tomography |
| P10 | 10 th percentile |
| P90 | 90 th percentile |
| PED | Pigment Epithelial Detachment |
| Q1 | 1 st quartile |

| Term | Definition / description |
|--------|--|
| Q3 | 3 rd quartile |
| q4w | Once in 4-weekly interval |
| RAGe | Report Appendix Generator system |
| SD | Standard Deviation |
| SD-OCT | Spectral Domain Optical Coherence Tomography |
| SHRM | Subretinal Hyper-Reflective Material |
| SMC | Safety Monitoring Committee |
| SoC | Standard of Care |
| SOC | System Organ Class |
| SRD | Single Rising Dose |
| SRF | Sub-Retinal Fluid |
| SUN | Standardization of Uveitis Nomenclature |
| TS | Treated Set |
| WHO-DD | World Health Organization Drug Dictionary |

3. INTRODUCTION

As per ICH E9 ([1](#)), the purpose of this document is to provide a more technical and detailed elaboration of the principal features of the analysis described in the protocol, and to include detailed procedures for executing the statistical analysis of the primary and secondary variables and other data.

This TSAP assumes familiarity with the Clinical Trial Protocol (CTP), including Protocol Amendments. In particular, the TSAP is based on the planned analysis specification as written in CTP Section 7 “Statistical Methods and Determination of Sample Size”. Therefore, TSAP readers may consult CTP for more background information on the study, e.g., on study objectives, study design and population, treatments, definition of measurements and variables, planning of sample size, randomization.

Study data (including data entered in the RAVE EDC system and external data provided by suppliers) will be stored in a Clinical Data Repository (CDR).

Pharmacokinetic (PK) parameters will be calculated using Phoenix WinNonlinTM software (version 8.1.1 or higher, [REDACTED]) or SAS Version 9.4 (or later version).

The statistical analyses will be performed within the validated working environment CARE, including SASTM (current Version 9.4, by [REDACTED] and a number of SASTM-based tools (e.g., macros for the analyses of AE data or laboratory data; Report Appendix Generator system (RAGe) for compilation/formatting of the CTR appendices).

4. CHANGES IN THE PLANNED ANALYSIS OF THE STUDY

All analyses as planned in CTP will be performed and are described in more detail in this TSAP.

The baseline definition of CTP was clarified in TSAP:

In CTP Section 5.1 it is '*For the endpoints, baseline is defined as the value at Visit 2; if not measured at Visit 2 then baseline is the value at Visit 1*'. If an actual time is given in the data, it will be checked whether the measurement at visit 2 was done before or after trial drug administration. If it is done after administration, the measurement will not be used as a baseline measurement. The baseline definition was updated to 'The baseline value is defined as the last measurement before first administration of BI 836880 (= value at V2, in case no actual time is given in data)'.

The definition of responder in further endpoints was clarified in TSAP. In CTP section 2.2.2, one of the further endpoints in MRD part is "Responder (yes/no) defined as absence of intra-retinal or sub-retinal fluid (IRF/SRF) or resolution of SHRM/PED in the study eye at Week 16 (Visit 6, cohort 3 only)". This definition is modified as: "Responder (yes/no) defined as resolution of IRF and SRF or resolution of SHRM/PED in the study eye at Week 16 (Visit 6, cohort 3 only)". To avoid redundancy, endpoint "Absence (yes/no) of intra-retinal or sub-retinal fluid (IRF, SRF) in the study eye at Week 16 (Visit 6, cohort 3 only)" and "Resolution (yes/no) of subretinal hyper-reflective material/retinal pigment epithelial detachment (SHRM/PED) in the study eye at Week 16 (Visit 6, cohort 3 only)" could be removed.

5. ENDPOINTS

The pharmacokinetic and pharmacodynamic parameters listed in Section 2.2 of the CTP for drug BI 836880 will be calculated according to the BI Standard Operating Procedure (SOP) ‘Standards and processes for analyses performed within Clinical Pharmacokinetics/ Pharmacodynamics’ [001-MCS-36-472] (4).

5.1 PRIMARY ENDPOINTS

Section 2.1.2 of the CTP:

SRD part:

- *Number of patients with ocular dose limiting events (DLEs) from drug administration until end of trial (EOT).*

For definition of DLEs, refer to [Section 7.4](#).

MRD part:

- *Number of patients with drug related AEs from drug administration until EOT.*

5.2 SECONDARY ENDPOINTS

5.2.1 Key secondary endpoints

This section is not applicable as no key secondary endpoints have been defined in the CTP.

5.2.2 Secondary endpoints

Section 2.1.3 of the CTP:

SRD part:

- *Number of patients with drug related AEs*
- *Number of patients with any ocular AEs in the study eye*

MRD part:

[figure not shown]
- *Percent change from baseline in Central Subfield Thickness (CSFT) in the study eye at Week 12 (Visit 5), for each dose*
- *Change from baseline in BCVA in the study eye at week 12 (Visit 5)*
- *Time to recurrence after the last treatment*
- *Number of patients with any ocular AEs in the study eye*

Boehringer Ingelheim
TRIAL STATISTICAL ANALYSIS PLAN
1336-0007

Page 10 of 36

c31147466-02

Proprietary confidential information © 2024 Boehringer Ingelheim International GmbH or one or more of its affiliated companies.

[figure not shown]

Boehringer Ingelheim
TRIAL STATISTICAL ANALYSIS PLAN
1336-0007

Page 11 of 36

c31147466-02

Proprietary confidential information © 2024 Boehringer Ingelheim International GmbH or one or more of its affiliated companies.

6. GENERAL ANALYSIS DEFINITIONS

6.1 TREATMENTS

For basic study information on treatments to be administered, assignment of dose groups, selection of doses, refer to CTP Sections 3 and 4.

The trial will consist of an SRD part followed by an MRD part. Both parts will be conducted open-label, non-randomized, and uncontrolled.

It was planned to assign up to 42 patients in total, up to 15 in the SRD part (5 sequential dose groups comprising 3 patients each) and 27 in the MRD part (11 patients in dose group 1 (first cohort) and 16 patients in dose group 2 (4 patients from cohort 2 and 12 patients from cohort 3)).

For details of dosage and formulation see Tables 6.1:1 and 6.1:2 below.

Table 6.1: 1 Treatments and labels used in the analysis – SRD part

| Dose group | Treatment | | Short Label |
|------------|-----------|--|-------------|
| 1 | A | BI 836880, 80 mg/mL solution, 0.06 mg, ivt | BI 0.06mg |
| 2 | B | BI 836880, 80 mg/mL solution, 0.18 mg, ivt | BI 0.18mg |
| 3 | C | BI 836880, 80 mg/mL solution, 0.5 mg, ivt | BI 0.5mg |
| 4 | D | BI 836880, 80 mg/mL solution, 1.0 mg, ivt | BI 1mg |
| 5 | E | BI 836880, 80 mg/mL solution, 2.0 mg, ivt | BI 2mg |

Table 6.1: 2 Treatments and labels used in the analysis – MRD part

| Dose group | Treatment | | Short Label* |
|------------|-----------|---|-----------------------|
| 1 | F | BI 836880 Concentrate for Solution for Injection 80 mg/mL, diluted with Diluent to 20 mg/mL solution, 1.0 mg, ivt | BI 1mg q4w – cohort 1 |
| 2 | G | BI 836880 Concentrate for Solution for Injection 80 mg/mL, diluted with Diluent to 40 mg/mL solution, 2.0 mg, ivt | BI 1mg q4w – cohort 2 |
| 3 | H | BI 836880 solution for injection 40 mg/mL, 2.0 mg, ivt | BI 1mg q4w – cohort 3 |

* cohort 1: resistant patients, cohort 2: naïve patients, cohort 3; frequently treated patients

Cohorts 2 and 3 are displayed separately although belonging to the same dose group.

Section 7.3.4 of the CTP:

For BI 836880, the residual effect period (REP) after IVT administration is not known. Therefore, all AEs with an onset between start of treatment and the respective EOT visit will be assigned to the on-treatment period for evaluation.

Thus, no follow-up period is considered in this trial. The following separate study phases will be defined for the analyses of AEs:

- **Screening** (ranging from 0:00h (midnight) on the day of informed consent until the first administration time of BI 836880)
- **On treatment**
 - **BI treatment** (separately for each treatment, ranging from the time of first administration of BI 836880 until 0:00h (midnight) on the day after trial completion date) – labelled with the short labels defined in tables above

The following AE displays will be provided in the report:

Section 15.3 and Appendix 16.1.13.1.8 (for ClinicalTrials.gov and EudraCT) of the CTR displays:

In these displays, the on-treatment phase will be analysed (labelled with the short label of the study treatment - the actual treatment is equal to the study treatment). Screening will not be included in this analysis. In Section 15.3, a total overall, on treatment phases included in this analysis ("Total") will be provided in addition.

In Section 15.4 and Appendix 16.2 (Listings) of the CTR displays, the screening period will be included, and no totals will be provided.

Tables of vital signs and laboratory values will present results for the above mentioned on treatment phase.

For detailed information on the handling of the treatments refer to the Technical TSAP ADS (analysis data set) plan and the Analysis Data Reviewers guide.

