	
For MRD cohort 3: Men and women over the age of 55 with active CNV secondary to wAMD that require frequent intravitreal (IVT) treatment (28 to 56 days between treatments) with ranibizumab, aflibercept, or bevacizumab for standard of care for at least 6 months, with the last IVT administration between 4-8 weeks before the first study drug administration.
 
Exclusion: Additional eye disease in the study eye that could compromise best corrected visual acuity.
 
For MRD cohort 3: Active intraocular inflammation in the study eye, > 0.5+ anterior chamber cell and/or vitreous haze grading, or history of intraocular inflammation in either eye with previous IVT administration(s), history of retinal vein occlusion, previous treatment with brolucizumab or faricimab, and/or medical history of autoimmune disease that has caused ocular inflammation.

Test product(s):	BI 836880
dose:	SRD Part: 0.06 mg, 0.18 mg, 0.5 mg, 1.0 mg, 2.0 mg (single doses) MRD Part: 1 mg (cohort 1) and 2 mg (cohort 2 and 3) (q4w)
mode of administration:	Intravitreal injection
Comparator products:	Not applicable
dose	Not applicable
mode of administration:	Not applicable
Duration of treatment:	SRD part: Single intravitreal dose MRD part: 3 intravitreal doses in 4-weekly intervals (q4w)
Endpoints:	
SRD part:
 
Primary endpoint:
 

Number of patients with ocular dose limiting events (DLEs)

 
Secondary endpoints:
 

Number of patients with drug related adverse events (AEs)

Number of patients with any ocular adverse events in the study eye

 
MRD part:
 
Primary endpoint:
 

Number of patients with drug related AEs

 
Secondary endpoints:
 

Percent change from baseline in CSFT in the study eye at Week 12 (Visit 5)

Change from baseline in best corrected visual acuity (BCVA) in the study eye at Week 12 (Visit 5)

Time to recurrence after the last treatment

	

Number of patients with any ocular adverse events in the study eye

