In case of clinical symptoms of hepatic injury (icterus, unexplained encephalopathy, unexplained coagulopathy, right upper quadrant abdominal pain, etc.) without lab results (ALT, AST, total bilirubin) available, the investigator should make sure these parameters are analysed, if necessary, in an unscheduled blood test. Should the results meet the criteria of hepatic injury alert, the procedures described in the DILI checklist should be followed.

According to ICH E3 ([15](#)), in addition to Deaths and serious adverse events, AEs classified as ‘other significant’ need to be listed in the clinical trial report. These will be any non-serious adverse event that led to an action taken with study drug (e.g., discontinuation or dose reduced or interrupted).

An overall summary of AEs (including number of patients with any AE, DLEs (applicable for SRD part and MRD part cohort 1 only), drug related AEs, procedure related AEs, ocular AEs, AESIs, serious AEs and drug related serious AEs) will be presented.

The frequency of patients with AEs will be summarized by treatment group/cohort, primary system organ class (SOC) and preferred term (PT). Separate tables will be provided for patients with ocular AEs, for patients with DLEs, for patients with serious AEs, for patients with drug-related AEs, for patients with drug-related serious adverse events, for patients with AESIs, for patients with drug-related AESIs and for patients with study procedure related AEs. In addition, the frequency of patients with AEs will be summarized by worst intensity, treatment group/cohort, SOC and PT.

The system organ classes will be sorted alphabetically, PTs will be sorted by frequency (within SOC).

In addition, frequencies of patients with non-serious AEs that have an incidence of $> 5\%$ for at least one treatment will be summarised by treatment, primary SOC and PT (both trial parts combined).

For disclosure of adverse events on EudraCT the following three entries will be created, combined for both trial parts:

- Adverse Events per arm for disclosure on EudraCT
- Non-serious Adverse Events for disclosure on EudraCT
- Serious Adverse Events for disclosure on EudraCT

For all ocular adverse events, ocular symptoms will be listed in addition.

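### SAP Table 6.1: 2 gives MRD cohorts 2 and 3 a 1 mg short label although their rows state 2.0 mg, and the SAP puts these labels on the AE and registry displays

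*SAP*

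**What the plan says.** SAP Section 6.1 lists eight treatments, A to E in the single rising dose (SRD) part and F to H in the MRD part, each with a description and a short label. For treatment G the entry reads "diluted with Diluent to 40 mg/mL solution, 2.0 mg, ivt | BI 1mg q4w – cohort 2". For treatment H it reads "BI 836880 solution for injection 40 mg/mL, 2.0 mg, ivt | BI 1mg q4w – cohort 3". In the other six rows, the label and the described dose agree.

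The protocol synopsis gives the MRD doses as "1 mg (cohort 1) and 2 mg (cohort 2 and 3) (q4w"). Protocol Section 3.1 also describes the second MRD part as 2 mg.

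SAP Section 6.1 then puts the labels to use. The on-treatment phase is "labelled with the short labels defined in tables above". In CTR Section 15.3 and the registry appendix, that phase is "labelled with the short label of the study treatment". On other safety outputs the SAP says: "Tables of vital signs and laboratory values will present results for the above mentioned on treatment phase". SAP Section 7.8.1 adds: "For disclosure of adverse events on EudraCT the following three entries will be created, combined for both trial parts".

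The same table numbers cohort 3 as dose group 3. The text above it puts cohorts 2 and 3 together in dose group 2, and the sentence below it says that they share a dose group.

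**The concern.** These labels are column headings for reported safety data, so the conflict is not confined to background text. The MRD primary endpoint is the number of patients with drug-related AEs, and its displays would carry the conflicting labels for two of the three cohorts.

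The displays that combine both trial parts are the most exposed. There the SRD labels `BI 1mg` and `BI 2mg` would stand beside three MRD labels that all begin `BI 1mg q4w`. The table footnote explains the cohorts by population (resistant, naïve, frequently treated) and not by dose. A registry reader would therefore see what looks like one repeated dose in three populations, with no multiple-dose data at 2 mg.

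**Working it through.** **Step 1: label against description, row by row (SAP Tables 6.1: 1 and 6.1: 2).**

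- A to E (SRD): 0.06, 0.18, 0.5, 1.0 and 2.0 mg. All five labels match.
- F (cohort 1): 1.0 mg, label 1 mg. Match.
- G (cohort 2): 2.0 mg, label 1 mg. Conflict.
- H (cohort 3): 2.0 mg, label 1 mg. Conflict.

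Two of eight labels conflict with their own row, both in the same way.

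**Step 2: are the row descriptions consistent with the rest of the documents?** Protocol Table 4.1.1: 1 gives an injection volume of 50 µl. Dose = concentration × volume:

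- F: 20 mg/mL × 0.05 mL = 1.0 mg
- G and H: 40 mg/mL × 0.05 mL = 2.0 mg

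The same protocol table also links 40 mg/ml with 2 mg per dose. The descriptions of G and H therefore agree with the synopsis, Section 3.1 and Table 4.1.1: 1 of the protocol. The short labels agree with none of these.

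**Step 3: head count (planned numbers, SAP Section 6.1).**

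- Dose group 2: 4 + 12 = 16, as the SAP states.
- MRD total: 11 + 4 + 12 = 27, as the SAP states. With 15 in the SRD part, 15 + 27 = 42, also as stated.
- Share under a conflicting label: 16/27 = 59.3%.

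**Step 4: displays combining both parts.** The SAP plans the SRD part as "5 sequential dose groups comprising 3 patients each".

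- Patients in rows stating 2.0 mg: 3 (E) + 4 (G) + 12 (H) = 19
- Of these, under a 2 mg label: 3/19 = 15.8%
- Under a 1 mg label: 16/19 = 84.2%

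**Step 5: was it corrected later?** The SAP history table for version 2.0 lists a document number, a table number, spacing and the history table itself. None of these touches Table 6.1: 2.

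**Step 6: what does not change.** Treatment codes and cohort suffixes remain distinct, cohorts 2 and 3 are shown separately, and analyses are by dose group/cohort. No patient moves between columns and no statistic changes. No instruction was found that puts the short label on the CSFT, BCVA or Kaplan-Meier outputs.

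**The case against.** The strongest reply is that this is an editorial slip without numerical consequence. Nothing is miscalculated, the suffix identifies each cohort, and anyone with the protocol can recover the dose. That is right about the estimates. It does not help a registry reader who sees only the label.

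The SAP also refers details of treatment handling to a technical analysis data set plan and a reviewers guide. Neither is available here, and they may already carry consistent labels. This limit stands: the consequence follows only if Table 6.1: 2 is used as written.

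The reach is also less direct for some outputs. The explicit order to use the short label in displays concerns the AE displays. For vital signs and laboratory values, the SAP says only that the tables present the same phase. Section 7.8.1 does not itself name the arm labels for the EudraCT entries; that link comes from Section 6.1.

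The 3/19 figure depends on three SRD patients at 2 mg. Protocol Section 7.1 asks for at least 6 treated patients at the final dose. With 6, the share under a 1 mg label would be 16/(6 + 16) = 16/22 = 72.7% instead of 84.2%. The MRD numbers are planned too, and the protocol calls them approximate. The percentages illustrate exposure to the label and do not measure an error in any result.

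Finally, the text around the table largely settles the dose-group number for cohort 3. It is a secondary point, but the cell still contradicts that text.

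**Conclusion.** The concern holds. As written, the SAP labels treatments G and H with a dose that contradicts their own rows and the protocol, and directs those labels onto the primary-endpoint AE displays and the registry appendix. This affects two of the three MRD columns, or 16 of 27 planned MRD patients (59%).

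The finding is a reporting inconsistency with no effect on any estimate, analysis set or patient assignment. It rests on planned patient numbers and on the outputs following Table 6.1: 2. It should be resolved before outputs are produced, because the labels reach public safety records and the change is small.

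**What to change.** Before outputs are produced:

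1. Reconcile the short labels for treatments G and H with the dose stated in their own rows and in the protocol.
2. Align the dose-group entry for cohort 3 with the surrounding text, which places it in the same dose group as cohort 2.
3. Check the analysis data set plan and the program formats for the AE, vital-sign, laboratory and registry displays, and carry the reconciled entries into them where they differ.
4. Record the change in the SAP history table.

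The cost is three table cells in the SAP and, if the programs reuse the present labels, one matching format. No analysis needs to be redesigned.

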6.2 IMPORTANT PROTOCOL DEVIATIONS

Important PDs will be reviewed at Medical Quality Review Meetings (MQRM) and/or TOM conducted periodically during the trial. For definition of important protocol deviations (iPD), and for the process of identification of these, refer to the Boehringer Ingelheim (BI) SOP "Identify and Manage Important Protocol Deviations (iPD)" ([10](#)).

Section 7.3 of the CTP: *Important protocol deviations (iPDs) will be defined in the Integrated Quality and Risk Management (IQRMP) plan.*

Categories which are considered to be iPDs in this trial were defined in the integrated quality and risk management plan (IQRMP) prior to trial initiation. The iPD list was transferred into the iPD specification file (due to changes in the SOP). Within this transfer some minor adaptations were made to comply with new naming conventions and categorizations.

IPDs will be identified no later than in the Report Planning Meeting, and the iPD categories will be updated as needed.

If any iPDs are identified, they are to be summarized into categories and will be captured in the decision log (16) and/or via iPD specification file (sdtm-dv-domain-specification) (12). Both documents will be stored within the TMF in EDMS.

The iPDs will be summarised and listed.

Table 6.2: 1 Important Protocol Deviations

| Category / Code | Description | Comment | Excluded from |
|------------------------|--|---|----------------------|
| A | Eligibility Criteria | | |
| A1 | Eligibility Criteria | Critical inclusion/exclusion criteria violated | No analysis sets |
| A2 | Eligibility Criteria | Withdrawal criteria as defined in the protocol met, but subject was not withdrawn | No analysis sets |
| B | Informed Consent | | |
| B1 | Informed Consent | Required Informed Consent not available/not done | All analysis sets |
| B2 | Informed Consent | Informed consent given late | No analysis sets |
| C | Trial Medication and Randomization | | |
| C1 | Trial Medication and Randomization | Incorrect dose injected | ERS |
| C2 | Trial Medication and Randomization | Treatment out of protocol defined window | ERS |
| D | Concomitant Medication | | |
| D1 | Concomitant Medication | Improper medication washout | ERS |
| D2 | Concomitant Medication | Prohibited medication use | ERS |
| E | Critical Study Procedure/Assessment | | |
| E2 | Critical Study Procedure/Assessment | OCT assessment out of window | ERS |
| F | Safety Procedures/SAE Reporting | | |

| Category / Code | Description | Comment | Excluded from | |
|------------------------|--------------------|--|---|------------------|
| | F1 | Safety Procedures/SAE Reporting | Critical safety procedure not followed | No analysis sets |
| G | | Privacy/Data Protection | | |
| | G1 | Privacy/Data Protection | Privacy and/or data protection violated | No analysis sets |
| Q | | Non-important COVID-19 Related | | |
| | Q1 | Non-important COVID-19 Related | Missed examination | No analysis sets |
| | Q2 | Non-important COVID-19 Related | Missed visit | No analysis sets |
| | Q3 | Non-important COVID-19 Related | Drug shipment | No analysis sets |

